1 BACKGROUND

While exploring structure-activity relationships of organic ligands possessing an N⁴O² donor core [1-3], we identified a gallium-68-radiopharmaceutical (named herein as ⁶⁸Ga-Galmydar) that demonstrates high extraction into the myocardium of mice, rats, and rabbits while also displaying efficient clearance from the blood pool. Additionally, [⁶⁸Ga]Galmydar is recognized by MDR1 P-glycoprotein (Pgp) [4] and Breast Cancer Resistance Protein (BCRP, ABCG2) [5] as their efficient transport substrate, and thus it exploits transporter-mediated excretion pathways from the blood and liver, resulting in high heart/blood and heart/liver ratios 60-minute post injection. Live cell-imaging of rat cardiomyoblasts using Galmydar (fluorescent probe) shows its localization within the mitochondria following permeation within cells indicating excellent correlation with radiotracer uptake data [4,5]. [⁶⁸Ga]Galmydar micro positron emission tomography (PET)/computed tomography (CT) imaging of rat and rabbit hearts show high myocardial uptake and high target/background contrast. Following ligation of the left anterior descending (LAD) coronary artery in rat and rabbits, PET/CT imaging clearly showed the hypoperfused region of the left ventricle wall. These hypoperfused regions of the myocardium correlated well to the same ex vivo regions by histochemical staining post imaging. [⁶⁸Ga]Galmydar has also shown sensitivity in monitoring ischemia caused by transient ligation of LAD in rabbits on PET imaging, also with positive correlation of the ischemic region with ex vivo histology. Radiation dosimetry studies in mice extrapolated to human dosimetry estimates using Medical Internal Radiation Dosimetry (MIRD) methodology and employing FDA guidelines (21 CFR 312) of maximum allowable dose to any organ of 50 mSV indicate an allowable maximum injection dose of 8 mCi in humans. This is comparable to ¹⁸F-Flurpiridaz, another myocardial perfusion imaging (MPI) agent undergoing Phase 3 studies. Importantly, [⁶⁸Ga]Galmydar does not demonstrate any remarkable clinical pathology (toxicology) in critical organs following intravenous administration of a single dose (1000 fold excess of an IV imaging dose) of an unlabeled agent into rats over 14 days. Finally, compared to ¹³N-ammonia (a positive control), [⁶⁸Ga]Galmydar also demonstrates similar radiotracer characteristics and, in particular, comparable myocardial first pass extraction of about 70-90% so that regadenosone-induced stress myocardial perfusion and myocardial blood flow (MBF) quantification employing kinetic modeling should be comparable [6,7,8]

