1.2 Study Rationale

1.2.1 Dosimetry Group

The successful implementation of [⁶⁸Ga]Galmydar in humans could provide a new mechanism-driven tracer for PET MPI, and successful realization of aims could ultimately take PET MPI to underserved regions nationwide and developing countries worldwide, where an ¹⁸F-distribution business model would have limitations. [⁶⁸Ga]Galmydar PET MPI could enable quantification of myocardial flow reserve (MFR= stress MBF / rest MBF that carries important diagnostic and prognostic information) that may play an additional important role to evaluate or monitor the effectiveness of preventive medical care or the treatment response on the function of the heart vessels in CAD individuals. These benefits combined with the minimal risks weight the ratio in favor of moving the PET radiotracer [⁶⁸Ga]Galmydar into human subjects. This component of the study will determine the biodistribution and calculate the radiation dosimetry of [⁶⁸Ga]Galmydar in normal healthy volunteers. Our radiation dosimetry studies in mice [9] extrapolated to human dosimetry estimates using MIRD methodology suggest an allowable maximum injection dose of 8 mCi in humans. The maximum Effective Dose for one 8 mCi intravenous administration of [⁶⁸Ga]Galmydar and three whole-body CT scans with CT attenuation scans results in a gender average radiation dose of 2.84 rem that is well within 57% of the allowable annual dose for radiation workers.

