4.4 Study Enrollment

Upon arrival to the imaging facility, participants will be provided the informed consent for review. The study coordinator will review the informed consent form with the participant and address any questions or concerns prior to obtaining written consent or performing any research procedures. Participants must be willing and able to undergo all procedures.

Imaging will begin with the healthy adult normal volunteers enrolled in the dosimetry group. The first two, (2) normal volunteers will be separated by 2-3 days to ensure participant safety data is ascertained during the post-injection phone follow-up. Upon completion of the review, the study will continue with imaging of the remaining dosimetry subjects with simultaneous entry of the rest/stress group.

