5.3 Drug Administration

The Sponsor-Investigator will adhere to the procedures and requirements in accordance with applicable policies of the Radiation Safety Committee (RSC) at Washington University and the U.S. Nuclear Regulatory Commission (NRC).

A PET-certified medical professional will draw, administer, and assay the dosage in a dose calibrator before and after the administration of all radiotracers.

The Dosimetry group will receive one single intravenous administration of $8 \text{ mCi} \pm 20\%$ (6.4–9.6 mCi) of ⁶⁸Ga-Galmydar. The Rest/Stress Group will receive two intravenous administrations of ⁶⁸Ga-Galmydar, $4 \text{ mCi} \pm 20\%$ (3.2–4.8 mCi) during rest and $6 \text{ mCi} \pm 20\%$ (4.8–7.2 mCi) during the stress of [⁶⁸Ga]Galmydar on the PET MPI Imaging Day-1. The acceptable mass for each [⁶⁸Ga]Galmydar administration is $\leq 10 \text{ } \mu\text{g}$. On Imaging Day-2, subjects will receive two single intravenous administrations each of $10 \text{ mCi} \pm 20\%$ (8–12 mCi) of N-13 Ammonia.

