6.4.1.2 Stress [⁶⁸Ga]Galmydar PET

- Perform all required safety assessments pre-injection of regadenoson and [⁶⁸Ga]Galmydar as described above. Monitor ECG rhythm and HR continuously during the PET scan;
- Administer a rapid (10-sec) regadenoson intravenous injection (0.4 mg/5 mL), followed by 5 mL saline flush;

- 30-sec post regadenoson injection, administer a maximum intravenous bolus injection of 6 mCi \pm 20% (4.8-7.2 mCi) with a mass of \leq 10 μ g of [⁶⁸Ga]Galmydar followed by a 10 mL normal saline flush. If the same IV line is used for both the regadenoson and radiotracer injection, wait 10 to 20 seconds after the normal saline flush post regadenoson injection before injecting the radiotracer;
- Begin up to a 30-min list-mode data acquisition for a single bed position at the level of the heart immediately post-injection;
- Perform all required safety assessments post-injection of ⁶⁸Ga-Galmydar, end of imaging and prior to discharge from the imaging facility as described above;
- Transfer participant to CTRU for post imaging assessments and procedures prior to discharge as described above.

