11.3.2.2 Rest/Stress Group

Participants will receive two [⁶⁸Ga]Galmydar intravenous administrations, 4 mCi during rest and 6 mCi during stress for the PET MPI performed on Imaging Day-1. The effective dose for a single intravenous administration of 6 mCi of [⁶⁸Ga]Galmydar is 0.62 rem and 0.41 rem for a 4 mCi administration performed. The acceptable mass of [⁶⁸Ga]Galmydar is \leq 10 μ g per administration. On Imaging Day-2, participants will receive two single administrations each of 10 mCi of ¹³N-Ammonia during the rest and stress PET MPI.

- Rest/Stress [⁶⁸Ga]Galmydar PET MPI**

The effective dose for a rest and stress PET MPI study includes an intravenous administration of 4 mCi during the rest PET and an 6 mCi administration during the stress PET MPI, and two CT-AC scans with topogram is 1.40 rem.

- Rest/Stress ¹³N-Ammonia PET MPI**

The effective dose for a single intravenous administration of 10 mCi of ¹³N-Ammonia is 0.07 rem. The effective dose for a rest/stress ¹³N-Ammonia PET MPI study includes two administrations each of 10 mCi of ¹³N-Ammonia and two CT-AC scans is 0.51 rem.

- Total Rest/Stress PET MPI**

The total effective dose for Imaging Day-1, rest/stress [⁶⁸Ga]Galmydar PET MPI and Imaging Day-2, rest/stress ¹³N-Ammonia PET MPI study is 1.91 rem. This includes one administration each of ⁶⁸Ga-Galmydar, 4.0 mCi during rest and 6 mCi during stress, and two CT-AC scans and two administrations each of 10 mCi of ¹³N-Ammonia and two CT-AC scans.

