12 DATA SAFETY MONITORING PLAN

In compliance with the Washington University School of Medicine Institutional Data Safety Monitoring (DSM) Plan, the PI will provide a DSM report to the IRB/HRPO annually. All members of the research team will review safety data as it becomes available. The DSM report will include, but not be limited to the protocol title, IRB protocol number, IND number, the activation date of the study, the number of subjects enrolled to date, a summary of all adverse events, number of subjects who dropped out/withdrew for any reason whether thought to drug related with a corresponding reason for dropout, and any new information related to the investigational drug or that may affect the safety or ethics of the study.

Drs. [name] (PI) and [name] and the Sponsor-Investigator, and at least one additional sub-investigator, will review and assess drug biodistribution and safety data through the 2-3 day post-injection phone follow-up from the first two (2) normal volunteers prior to imaging of the remaining normal volunteers. Upon completion of the review, the study will continue with imaging of the remaining dosimetry subjects with simultaneous entry of the rest/stress group. Asymptomatic normal controls and symptomatic patients who have undergone a SPECT MPI examination that is normal or positive and prior to ICA intervention, will undergo a rest/stress [⁶⁸Ga]Galmydar PET MPI and rest/stress ¹³N-ammonia PET MPI with a minimum of a 3-day separation.

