- j) PET/CT imaging: Obtain a low-dose CT-AC (50 mAs) prior to each rest and stress radiotracer injection. If the same IV line is used for both the regadenoson and radiotracer injections, wait 10-20 sec after the normal saline flush post regadenoson injection before injecting the radiotracer.

k) [⁶⁸Ga]Galmydar Imaging Day-1:

- *Rest PET*: Administer 4 mCi ±20% (3.2–4.8 mCi) of [⁶⁸Ga]Galmydar IV injection followed by a 10 mL saline flush and immediately begin up to a 30-min list-mode data acquisition for a single bed position at the level of the heart. The interval between the rest and stress [⁶⁸Ga]Galmydar PET acquisitions *should be no less than 2 hours and no greater than 4 hours*.
- *Stress PET MPI*: Administer a rapid (10-sec) regadenoson IV injection (0.4 mg/5 mL), followed by 5 mL saline flush; 30-sec post regadenoson injection, administer 8 mCi ±20% (6.4–9.6 mCi) of [⁶⁸Ga]Galmydar IV injection followed by a 10 mL saline flush. Begin up to a 30-min list-mode data acquisition for a single bed position at the level of the heart.

l) ¹³N-Ammonia Imaging Day-2:

- *Rest PET*: Administer an IV bolus injection of 10 mCi ±20% (8–12 mCi) of ¹³N-Ammonia followed by a 10 mL saline flush and immediately begin a 10-min list-mode data acquisition (if the anterior-posterior diameter of the chest is >50cm increase to 15-min) for a single bed position at the level of the heart. The interval between the rest and stress ¹³N-ammonia acquisitions should be *no less than 1-hour*.
- *Stress PET MPI*: Administer a rapid (10-sec) regadenoson IV injection (0.4 mg/5 mL), followed by 5 mL saline flush; 30-sec post regadenoson injection, administer 10 mCi ±20% (8–12 mCi) of ¹³N-Ammonia IV bolus injection followed by a 10 mL saline flush. Begin a 10-min list-mode data acquisition (if the anterior-posterior diameter of the chest is >50cm increase to 15-min) for a single bed position at the level of the heart.

m) Transfer [⁶⁸Ga]Galmydar participants to CTRU for post imaging safety assessments and discharge.

Discharge ¹³N-Ammonia participants from the CCIR.

n) Contact [⁶⁸Ga]Galmydar participants by phone within 2-3 days post [⁶⁸Ga]Galmydar injection.

[⁶⁸Ga]Galmydar and ¹³N-ammonia imaging visits will be separated by a minimum of 3-days and not before the follow-up phone call is complete for capturing participant adverse events following the administration of [⁶⁸Ga]Galmydar. If any of the days are not business days, the phone call may occur the following business day.

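### Table 3 footnote k gives the Galmydar stress injection as 8 mCi (6.4–9.6), against 6 mCi (4.8–7.2) in the body of the protocol; the footnote is the wrong entry

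*Combined protocol and SAP*

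**What the plan says.** The Galmydar stress activity for the rest/stress group appears in four places.

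- **Section 5.3 (Drug Administration):** 6 mCi ±20%, with the range given as "4.8–7.2 mCi) during the stress of [⁶⁸Ga]Galmydar on the PET MPI Imaging Day-1".
- **Section 6.4.1.2 (the stress scan procedure):** staff are to "administer a maximum intravenous bolus injection of 6 mCi", again with ±20% and 4.8–7.2 mCi.
- **Section 11.3.2.2 (radiation exposure):** "4 mCi during rest and 6 mCi during stress for the PET MPI performed on Imaging Day-1". The effective doses stated there are 0.41 rem for the 4 mCi injection, 0.62 rem for the 6 mCi injection, 1.40 rem for the Galmydar study with two attenuation CTs, and 1.91 rem once the ammonia study is added.
- **Section 16, Table 3, footnote k:** "administer 8 mCi ±20% (6.4–9.6 mCi) of [⁶⁸Ga]Galmydar IV injection".

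Section 6 refers the reader to the schedule tables as the summary of study procedures. Section 5.3.1 requires an authorized user physician to approve, before administration, any dosage outside the allowable range.

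**The concern.** Two different acceptable ranges are in force for the same injection of an agent with no prior human data. Each entry is internally consistent (8 × 1.2 = 9.6; 6 × 1.2 = 7.2), so this is not a slip in a single digit or a text-extraction fault. Nothing in the protocol says which place takes precedence.

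The dose-calibrator assay in Section 5.3 does not protect against the error, because the range that the assay is checked against is what differs. The authorized-user variance has the same weakness: it applies only when someone recognises that the dosage is out of range. The conflict also runs the other way. A correct 6 mCi injection lies below Table 3's lower bound of 6.4 mCi and would look like an under-dose.

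At stake are how much radioactivity participants receive, whether out-of-range injections are caught, and whether the effective dose stated in the protocol is the one delivered. Stress activity that varied with the page consulted would also add avoidable variation to the images being compared with ammonia.

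**Working it through.** **Inputs.** Section 11.3.1: 0.18 rem per single-bed attenuation CT. Section 11.3.2: 0.103 rem/mCi for Galmydar and 0.007 rem/mCi for ammonia. Section 11.3.2.2: two attenuation CTs per imaging day, 4 mCi at rest, and two ammonia injections of 10 mCi.

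**Formulas.** Galmydar day = (rest mCi + stress mCi) × 0.103 + 2 × 0.18. Ammonia day = 20 × 0.007 + 2 × 0.18.

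**Step 1: reproduce the stated doses, and see which stress activity they rest on.**

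| Quantity | Stated (rem) | With 6 mCi | With 8 mCi |
|---|---|---|---|
| Stress injection | 0.62 | 6 × 0.103 = 0.618 | 8 × 0.103 = 0.824 |
| Galmydar day | 1.40 | 10 × 0.103 + 0.36 = 1.39 | 12 × 0.103 + 0.36 = 1.60 |
| Ammonia day | 0.51 | 0.14 + 0.36 = 0.50 | 0.50 |
| Total | 1.91 | 1.89 | 2.10 |

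The 6 mCi column agrees with the stated figures to within 0.02 rem, which rounding and the topograms could account for. The 8 mCi column misses by about 0.2 rem in every row where the stress activity enters. The radiation section was therefore calculated from 6 mCi, as Sections 5.3 and 6.4.1.2 would lead one to expect.

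**Step 2: activity if Table 3 is followed.** Nominal: 8/6 = 1.33. Upper end: 9.6/7.2 = 1.33. Both are 33% above the body text.

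**Step 3: overlap of the two ranges.**

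- 4.8 to below 6.4 mCi: in range under Section 5.3, below range under Table 3.
- 6.4 to 7.2 mCi: in range under both.
- Above 7.2 to 9.6 mCi: above range under Section 5.3, so a variance is needed under Section 5.3.1; in range under Table 3.

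**Step 4: effective dose if Table 3 is followed.** The extra is (8 − 6) × 0.103 = 0.206 rem. Added to the stated total, 1.91 + 0.206 = 2.116, or about 2.12 rem; 0.206/1.91 = 10.8%. Starting from the recomputed 1.89 instead gives 2.10 rem, so the choice of base hardly matters. At the upper ends the stress injection alone is 9.6 × 0.103 = 0.99 rem against 7.2 × 0.103 = 0.74 rem.

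**The case against.** The best defence is that Table 3 only summarises. Section 5.3 is the drug-administration section, Section 6.4.1.2 is the step-by-step procedure, and both agree with the radiation section. Trained staff may well dose from those, and nothing shows that anyone would work from the footnote. The radiation consequence is also modest. Even with every Table 3 activity at its upper tolerance, the total is 14.4 × 0.103 + 24 × 0.007 + 4 × 0.18 = 2.37 rem, below the 2.81–2.87 rem that Section 11.3.2.1 states for the dosimetry volunteers.

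This limits the likely harm but leaves the conflict in place. Schedule tables are there to be worked from, and the footnote is written as a dosing instruction with its own tolerance.

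A reader might infer two stronger points that the documents do not support.

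- **That Table 3 causes a breach of the 8 mCi limit.** Section 1 derives that figure from a "maximum allowable dose to any organ of 50 mSV indicate an allowable maximum injection dose of 8 mCi in humans", and Section 1.2.1 repeats that the mouse data "suggest an allowable maximum injection dose of 8 mCi in humans". A 9.6 mCi injection is numerically above 8 mCi. But the protocol deliberately prescribes the same 6.4–9.6 mCi range to the dosimetry group (Sections 5.3, 6.3 and 11.3.2.1, and Table 2 footnote i). An injection of 9.6 mCi is therefore not peculiar to Table 3, and correcting the footnote would not remove it.
- **That the rest/stress group opens without an adequate dosimetry check.** Under Section 4.4, after the first two volunteers, "the study will continue with imaging of the remaining dosimetry subjects with simultaneous entry of the rest/stress group". Section 12 already says that the investigators "will review and assess drug biodistribution and safety data through the 2-3 day post-injection phone follow-up from the first two (2) normal volunteers". A numerical organ-dose estimate at that point is not required, but its absence contradicts nothing in the plan. The limit is worded as an injection dose, and the upper ends of the body-text rest and stress injections (4.8 and 7.2 mCi) are both below 8 mCi. The documents give no organ-dose coefficient from which to show a problem. An early organ-dose calculation is at most an optional suggestion.

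**Conclusion.** Table 3 footnote k is wrong as written. Three sections give 6 mCi, one of them as a maximum, and the protocol's own effective doses reproduce only with 6 mCi. Followed literally, the footnote means 33% more stress activity, a band above 7.2 and up to 9.6 mCi in which the required variance would not be triggered, and a total of about 2.12 rem rather than 1.91 rem (+11%).

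The effective-dose figures use the protocol's 0.103 rem/mCi and assume that dose scales linearly with activity. That 6 mCi is the intended value is an inference from the agreement of the other sections and the dose arithmetic, and a strong one. The conclusion goes no further than this conflict: it does not show that any limit is exceeded or that the two-volunteer review is deficient.

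**What to change.** Change the stress entry in Table 3 footnote k to 6 mCi ±20% (4.8–7.2 mCi), so that it matches Sections 5.3, 6.4.1.2 and 11.3.2.2. Carry the same correction into any dose order, worksheet or case report form that was built from Table 3.

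The cost is one line in one table, submitted as an amendment through the usual approvals. Nothing changes in the design, the sample size, the imaging schedule or the stated radiation doses, which already assume 6 mCi. If any stress scans have already been done, checking the recorded activities against 4.8–7.2 mCi would show whether the footnote was ever followed.
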